8.3.2 Statistical Analysis (Aim 2)

Analysis will follow the general approach and then the same specific approach as described for Aim 1, looking at differences in outcomes among groups utilizing generalized linear models. Using this methodology we will be able to examine the differences over time baseline to post recovery, examining the change between time points adjusting for baseline and the interaction between time and group. The secondary approach would examine the difference among groups adding covariates,

accounting for age, gender and other potential covariates such as number of prior surgeries, length of time in surgery and type of surgery (burn related or other).

Using our validation information for the OPAS pain assessment scale¹⁰⁷ with 48 subjects per group, we have a power of $\geq 80\%$ to detect a reduction in pain scale of 0.4 given the standard deviation of 0.52, using a type I error rate of 0.016 (to account for the multiple testing) and 2-sided test. Given the 0.3 difference in pain reduction between preverbal and nonverbal in the validation study, the expected difference appears reasonable. Similarly using prior work performed at our hospital¹⁰³ which examined the rate of postoperative nausea and vomiting after reconstructive burn surgery, with 46 subjects per group we would have 80% power to detect a difference of 69% in the control versus 40% in the HT group with a 2-sided test and type I error rate of 0.05. However after accounting for the multiple testing, using type I error rate of 0.016, the power is reduced to 70% with the 50 subjects per group estimated for the proposed study. Turner et al²⁰ reported on pain after dressing change in older adolescents and adults. In their randomized trial of therapeutic touch; a 23% decrease in anxiety was detected in the intervention group. If we assume that we will see this level of decreased anxiety in the HT group compared to the control and also assume an effect size of 0.7 and a type I error of 0.16, the 50 subjects per group (estimated for Aim 1) would yield 85% power for our analysis of anxiety.

8.3.3 Statistical Analysis (Aim 3)

The data analytic plan will follow that established for Aims 1 and 2 using a general linear model and use of the appropriate link function dependent upon outcome. Satisfaction variables are notoriously skewed in distribution and so may need to be dichotomized for analysis. Data analysis will be performed in a blinded fashion with regards to the subject and any group assignment. The analysis of cost will include examination of cost to charge ratio (CCR). Because cost fluctuates over time, the annual cost to charge ratio (obtained from Shriners Headquarters) will be used to calculate and apply CCR to charges pertinent to this study in order to determine if the expense of a 1 hour HT session translates to a change in dollars expended in PACU care, total length of hospital stay and morbidity treatment costs (ex. anxiety/pain/itch/anti-nausea medication expense). Cost-benefit analysis comparing those with HT versus no HT and by group will be conducted. An expert in health cost/economics will be consulted where necessary for the latter analysis.

Unfortunately we have no published data with respect to satisfaction or cost analysis. We will be able to detect an effect size of at least 0.66 with a sample size of 50 per group and accounting for multiple testing, with a 2-sided test, a type 1 error rate of 0.016 and power is 80%. A power of 80% could be maintained with correlations as low as $r=0.20$.

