8.0 Statistical Considerations

- 8.1 All data will be managed and analyzed using SAS® Version 9.3 (SAS Institute, Cary, NC) unless otherwise stated for specialized analysis. Demographic and summary data will be compiled and entered into the SAS research database by a

trained data manager. The database has been in use for 14 years; it will be adapted for data entry specific to the new project. The database is stored on SHC's dedicated network drive. The network is security- and backup- protected by SHC information systems on a daily basis. In addition, the individual study files are password protected. The programs are run by the statistician and verified by a research investigator. Prior to embarking on any analysis, variables will be checked for outlying values. Distributional properties of the continuous variables will be examined and any transformations necessary for analysis considered. Bivariate comparisons will follow, to look at differences in baseline variables between HT and control groups (ex. age, gender and race, also length of time and type of surgical procedure e.g. burn versus other reconstructive procedure). These latter variables are potential covariates for secondary analysis. Analysis of variance (ANOVA) or Kruskal-Wallis test and Chi-square analysis will be used for these comparisons. Similarly, the association between outcome variables and baseline variables will be examined; correlation and ANOVA or Kruskal-Wallis will be used as appropriate.

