The measures targeted are TST, sleep efficiency, REM sleep and WASO. This Table shows data from a pilot cross-over study (median and 25th and 75th percentile) for the sleep variables of interest for 15 study subjects. In order to see the HT group with longer TST than the other groups, we will need a sample size of 50 per group for 80% power to detect a difference of 35 minutes, standard deviation of 70, assuming a 2-sided test and type I error rate of 0.016 to account for multiple testing. Similarly for sleep efficiency, we hypothesize a difference of 2% whereas in a previous study we observed a difference of 10%.³¹ Using the sample size of 50 per group we would be able to detect a difference of 7% with a standard deviation of 15, 2-sided test and type I error rate of 0.016, to account for comparing HT to the 3 control groups. Because the percentages depend upon another time dependent variable, the power is based on REM minutes. Using REM minutes, 50 subjects per group would enable us to detect a 15 minutes difference in REM sleep, assuming a standard deviation of 30, power of 80% and a 2-sided test. For WASO, with an assumed standard deviation of 50, a type 1 error rate of 0.016, a power of 80% and a 2-sided test, a difference of 25 minutes will require 50 subjects in each group, producing a total sample size of 200 subjects.

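### The 80% power stated for satisfaction (effect size 0.66) fits an undivided score and does not carry over if the score is dichotomized, which the same section allows

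*Combined protocol and SAP*

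**What the plan says.** Section 8.3.3 plans the Aim 3 analysis "using a general linear model and use of the appropriate link function dependent upon outcome". On satisfaction it adds: "Satisfaction variables are notoriously skewed in distribution and so may need to be dichotomized for analysis". The only power statement for this aim covers satisfaction and cost together: "We will be able to detect an effect size of at least 0.66 with a sample size of 50 per group", at two-sided alpha 0.016 and 80% power. The authors acknowledge that they have no published satisfaction or cost data. The section gives no response scale, SD, expected proportion satisfied or cut-point, and no rule for deciding whether to cut.

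The alpha comes from section 8.3.1: "type I error rate of 0.016, to account for comparing HT to the 3 control groups". The group size also comes from there; the last of the Aim 1 calculations "will require 50 subjects in each group, producing a total sample size of 200 subjects".

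Section 4.2 describes the survey as questions on the HT procedure and on sleep, plus four Press Ganey items. It defines no total score.

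**The concern.** One section describes two possible forms of the satisfaction endpoint and gives power for only one. A standardized difference of 0.66 describes a shift in means. A binary endpoint needs two proportions, and none are given. The plan does this properly elsewhere: section 8.3.2 powers nausea and vomiting as 69% versus 40% and admits that power drops to 70% at alpha 0.016. Satisfaction, which the authors think may become binary, has no such statement.

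A reader of a null satisfaction result would assume that the trial had 80% power for a moderately large effect. If the score had been split, that could be well wrong. With neither the decision to split nor the cut-point fixed, the endpoint itself also stays open until the data are seen.

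**Working it through.** **Inputs.** From section 8.3.3: effect size 0.66, n = 50 per group, two-sided alpha 0.016, power 80%. Alpha is 0.05/3 = 0.0167, stated as 0.016, for three comparisons with HT (section 8.3.1). The control proportion is not in the documents, so it is varied below as an assumption.

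**Step 1: the plan's own figure.** Two-sample t-test with 98 degrees of freedom. Noncentrality = 0.66 × √(50/2) = 3.30; critical value t = 2.451. Power from the noncentral t is 80.0%, and the detectable difference at 80% is 0.660 SD. The figure is therefore correct for a comparison of means.

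**Step 2: check of the two-proportion formula.** With d = |p1 − p2| and p̄ the mean of p1 and p2:

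power = Φ[(d − z·se0)/se1], where z = 2.409, se0 = √(p̄(1 − p̄)·2/50) and se1 = √((p1(1 − p1) + p2(1 − p2))/50).

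For nausea and vomiting, 69% versus 40% gives 70.0%, which matches section 8.3.2.

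**Step 3: the same 0.66 shift, cut in two.** Assume a normal latent score, a control share pc in the top class, and an HT share pt = Φ(Φ⁻¹(pc) + 0.66).

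Example with pc = 0.50: pt = Φ(0.66) = 0.745, d = 0.245, p̄ = 0.623, se0 = 0.0969, se1 = 0.0938. Power = Φ[(0.2454 − 2.409 × 0.0969)/0.0938] = Φ(0.126) = 55%.

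| Control top class | HT top class | Power, 50 per group | n per group for 80% |
|---|---|---|---|
| 37% | 63% | 57% (maximum) | 78 |
| 50% | 74.5% | 55% | 82 |
| 60% | 82% | 50% | 89 |
| 70% | 88% | 43% | 105 |
| 80% | 93% | 32% | 136 |
| 85% | 95.5% | 26% | 167 |
| 90% | 97% | 18% | 228 |

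**Step 4: detectable proportions, with no latent model.** Solving the Step 2 formula for 80% power at 50 per group:

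- 50% versus 80.5%
- 60% versus 88%
- 70% versus 94.5%
- 80% versus 99.5%

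From a control rate of 85%, even an HT rate of practically 100% gives only Φ[(0.15 − 2.409 × 0.0527)/0.0505] = 68%.

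On the latent scale, the first three pairs correspond to shifts of 0.86, 0.93 and 1.07 SD, against the stated 0.66.

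**The case against.** **The size of the loss depends on what 0.66 means.** A reader might infer that a dichotomized satisfaction endpoint simply has 26% to 55% power. The documents do not support that. The range needs a latent normal score and a control rate of 50% to 85%, and neither is stated. A normal latent score also sits uneasily with the skew that prompts the cut. The text says only effect size:

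- Read as Cohen's h, power is about 81% by the arcsine approximation.
- Read as a standardized difference on the binary scale itself, power is 78%.
- For an assumed top-heavy 5-point item with 0.66 on the observed score, a top-box split has about 81% to 87% at control rates of 50% to 70%.

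This stands against any unconditional figure. It does not rescue the plan's statement. The exact t-test match favours the comparison-of-means reading, and under Cohen's h the differences are as large as those in Step 4 and are nowhere disclosed.

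**Dichotomizing is only a contingency.** This is correct. The plan does not commit to it, and the link-function wording leaves room for a binary model. But allowing the model does not supply its power or its cut-point.

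**The cut-point could be tuned to the result.** A reader might infer this, but section 8.3.3 says the analysis is blinded to group, and section 4.1.1 blinds the analysing biostatistician. A cut set on pooled, blinded data is not selected for a treatment effect. What remains is that the endpoint is not fixed beforehand.

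**Rank methods are already planned.** They are, but not for this comparison. The sentence in section 8.1, "Analysis of variance (ANOVA) or Kruskal-Wallis test and Chi-square analysis will be used for these comparisons", concerns baseline differences, and the one after it concerns associations of outcomes with baseline variables. The better support for an undivided analysis is the link-function clause.

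**Conclusion.** The point holds as a mismatch between the stated power and one permitted form of the endpoint. The 80% at 0.66 is right for an undivided, roughly normal score and is not a power statement for a dichotomized one.

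Under a latent-normal 0.66 SD shift, no cut reaches more than about 57%, and the loss grows as more controls fall in the top class. The firmer statement, which needs no latent model, is that 50 per group at alpha 0.016 detects only differences of roughly 25 to 30 percentage points from control rates of 50% to 70% (80.5 − 50 = 30.5; 94.5 − 70 = 24.5). From 85% it cannot reach 80% power at all. Whether control satisfaction will be that high is not stated.

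The consequence is limited. Section 2.3 makes satisfaction part of an additional secondary objective, and the total of 200 rests on Aim 1. The correction is still worth making because it costs only wording.

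**What to change.** In section 8.3.3:

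- Replace the dichotomization sentence with an undivided ordinal analysis of the satisfaction responses: a generalized linear model with cumulative-logit link, which the existing link-function wording allows, or a Wilcoxon test of HT against each control group. Report the percentage giving the top response descriptively.
- State that 80% power at 0.66 applies only to an undivided, approximately normal score, and that power will be lower when responses pile up at the ceiling.
- If any item is still to be dichotomized, name the item, fix its cut-point before data are seen, and give the detectable difference in proportions, as section 8.3.2 does for nausea and vomiting.

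The plan should not insert a replacement power figure for skewed ordinal responses, because that would rest on assumed response distributions and item correlations. It should not introduce a sum score that the documents do not define.

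The cost is a less favourable stated power and odds ratios that are slightly harder to present than percentages. Enrolment, randomization and the primary analysis do not change.

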9.0 Study Finance

9.1 Funding Source

This study is financed through a grant from the Shriners Hospitals for Children, North America.

9.2 Participant Stipends or Payments

A gas card valued at \$20 will be provided to study participants (or families) as compensation for time or travel.

